9.3 Interim analyses and Stopping Rules

No interim analysis will be conducted on primary or secondary outcomes. The DSMB is granted full power to recommend discontinuation of the study to the consolidated IRB if safety concerns are found. The board will meet prior to each flu season RCT implementation to review patient safety and adverse events. The DSMB members will determine the cadence of future meetings and/or safety reports. Following each meeting/report, the board will make recommendations to the IRB as to whether the study should continue or if changes to the protocol are needed.

9.4 Outcomes

9.4.1 Primary outcome

End of season influenza vaccination status based on California's statewide vaccine registry (CAIR2).

9.4.2 Secondary outcomes

Vaccination intentions as measured by patients' contact with appointment systems, scheduled vaccination appointments (and missed appointments), and influenza hospitalizations among patients that are eligible to receive vaccinations.

9.5 Data Analyses

Statistical Analysis Plan

We will perform separate evaluations of the impact of the text enhancements (callback and bidirectional texting) on the one hand, and transportation messaging on the other hand. Primary outcomes will be evaluated as a test of differences between proportions vaccinated in control and treatment groups, and heterogeneity of treatment effects will separately analyze subgroups. For further analyses, we will use multivariable log-binomial regression models with vaccination status at the end of the campaign as the outcome variable. Regressions will include indicators for each intervention as fixed effects, with the standard text condition as the reference group, and potentially clinic random effects, depending on retrospective analysis results. Models will also adjust for patient age, gender, race/ethnicity, insurance, and whether the patient was vaccinated in at least one of the prior two flu seasons. Secondary analysis will include subgroup interactions with intervention indicators to assess heterogeneity of treatment effects. In exploratory analyses, we will investigate interactions between interventions, questions related to modality of message delivery, as well as whether encounter type, click rates on messages, and distance to the health care facility from the home address affect influenza vaccination rates.

In addition, we will evaluate the loss to follow-through rates (scheduling an appointment, but did not complete the appointment) by patient demographics, as distance to the health care facility from the home address).

For the evaluation of text enhancements, we will perform a 3-fold Bonferroni correction accounting for pairwise comparison of intervention arms, using a two-sided significance level of 0.017. For the evaluation of transportation messaging, we will use a two-sided significance level of 0.05. All analyses will be intention-to-treat, and will be performed using SAS v. 9.4 (SAS Institute Inc., Cary, NC).

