4. SELECTION AND ENROLLMENT OF PARTICIPANTS

4.1 Inclusion Criteria

All patients over six months old that are members of an LACDHS managed care plan and have had contact with the health system in the past 2 years are eligible for LACDHS vaccination campaigns. In 2022, this includes over 273,000 patients.

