4.2 Exclusion Criteria

The exclusion criterion is a patient age of < 6 months, as babies less than 6 months are not eligible for influenza vaccination. We will also exclude individuals who have already received their flu vaccination this season.

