5. STUDY INTERVENTIONS

5.1 Interventions, Administration, and Duration

Text messages will begin to be sent at the beginning of the 2022 flu season. We will randomly spread out the calls throughout the day and week in order to minimize unnecessary overload for the call center when patients text back a “1” response that they would like a

call or text message to help them. We can do this by randomizing patients into batches so that there is no systematic time-of-day or day-of-week for any patients. We will send up to 3 reminders this flu season.

Control arm: Standard Texts (n=232,950). Patient randomized to this study arm will receive up to 3 text messages, reminding them about the importance of influenza vaccination. The messages themselves are shown below. The standard texts will include a clinic call back number and patient portal self-scheduling for patients to schedule their influenza vaccines. The direct scheduling texts includes a direct number to an agent that can help schedule and answer questions on the phone in real time. The texts with a direct number to schedule will link a specified phone number to call and schedule. This number would be answered by a central agent quickly and a patient could schedule their flu shot at any clinic site. This specific phone number would not go through the multiple option menus a patient would normally experience when calling their clinic.

Intervention arm: Standard Texts with Transportation (n=3,050). The standard texts with transportation includes phone number for patients to reserve transportation to a vaccination appointment based on Medi-Cal health plan transportation resources.

Prepped Text Messages for DHS Flu Campaign 2022 - 2023

Standard Text:

#PCM#H: #FirstName#, your flu shot is ready! Call your clinic at #ExternalRefNo# or visit the LA Health Portal at <http://bit.ly/BookFluShot> if you want this shot held for you.

Standard Texts (+ Transportation)

#PCM#H: #FirstName#, your flu shot is ready! Call your clinic at #ExternalRefNo# or visit the LA Health Portal at <http://bit.ly/BookFluShot> if you want this shot held for you. You can call #Health Plan Phone Number# to schedule a free ride your flu shot through #Health Plan Name#

Examples (Transportation)

- Standard Texts (+ Transportation) - LA Care**

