6.2.2 Enrollment, Baseline, and/or Randomization

Enrollment

Identification of families (i.e., households): We will group families using one of two possible methods. First, LACDHS has an identifier that ties family members together. It is called the "Family Budget Unit." We will explore this method. If it does not work, we will use another method that we have utilized successfully in the UCLA-based study from which this study is derived. We will assume that people living in the same address belong to the same family. As a secondary measure, we use a

telephone number as a linking number (i.e., if two people have the same telephone number, we assume they are from the same household).

Baseline Assessments

Vaccination status. We will assess baseline vaccination status at the beginning of the flu season as we will exclude individuals who have already received their vaccination.

Randomization

We will randomly allocate families to one of the study arms shown above and send family members the allocated text message. All family members will therefore receive the same text message. This is meant to reduce confusion among patients. For the analysis, we will randomly select one index patient per household for analysis. This follows Cochrane criteria for being included in meta-analyses. We will attempt to affiliate index patients with practices, and randomize patients (families) within these practices.

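### The primary test is an unadjusted difference in proportions although the plan already names prior-season vaccination as a covariate; the test is valid but gives up some precision in the 3,050-patient transportation arm

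*Combined protocol and SAP*

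**What the plan says.** Section 9.5 (Data Analyses) defines the primary evaluation in one sentence: "Primary outcomes will be evaluated as a test of differences between proportions vaccinated in control and treatment groups". No covariate or stratum is attached to that test. A multivariable log-binomial model follows, assigned to further analyses. Of it the section says "Models will also adjust for patient age, gender, race/ethnicity, insurance, and whether the patient was vaccinated" in at least one of the two preceding flu seasons. Clinic may enter that model, but only as "potentially clinic random effects, depending on retrospective analysis results".

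Other sections bear on this point:

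- Section 6.2.2 randomises families and says "We will attempt to affiliate index patients with practices, and randomize patients (families) within these practices". For the analysis, "we will randomly select one index patient per household for analysis".
- Section 5.1 gives 3,050 patients for standard texts with transportation and 232,950 for standard texts. Section 9.5 tests this comparison at a two-sided 0.05.
- Section 9.2 claims 80% power for a 2% impact of each intervention. It gives neither the control rate nor whether the 2% is absolute or relative. The only LACDHS vaccination rate in the documents is 31.2%, in the background (section 2.1).
- Section 4.2 adds: "We will also exclude individuals who have already received their flu vaccination this season".

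**The concern.** Whether someone was vaccinated in recent seasons is an obvious candidate predictor of whether they will be vaccinated this season. The plan evidently agrees, since it lists that variable. Yet the test that decides the trial ignores it, and the information is used only in a supporting model on a different scale (a risk ratio).

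This does not make the primary test wrong. Families are randomised and one person per household is analysed, so the simple comparison is unbiased and its type I error is sound. The loss is in efficiency, and it falls on the arm that can least afford it. A control group of 232,950 cannot make up for the sampling error of 3,050 treated patients. If power for the transportation comparison is below the 80% claimed, precision available from covariates already in the planned model should be used in the primary test.

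There is also a smaller gap in pre-specification. Whether practice belongs in the analysis should follow from how families were randomised, but section 9.5 leaves it to the results of the retrospective analysis.

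**Working it through.** **Inputs.** From the documents: n_C = 232,950 and n_T = 3,050 (section 5.1); two-sided α = 0.05 (section 9.5); claimed power 80% for a 2% impact (section 9.2); LACDHS rate 31.2% (section 2.1). Assumed: the 2% is absolute; 31.2% or a lower figure is the control rate; the section 5.1 numbers are analysed index patients; R², the share of outcome variance explained by the baseline covariates, lies between 0 and 20%.

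**Step 1. The plan's own power figure.** With the pooled two-proportion test,

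power = Φ[(d − 1.96·SE₀) / SE₁],

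where SE₀ uses the pooled rate and SE₁ the two separate rates. At 31.2% against 33.2%:

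- pooled rate = 0.3123, SE₀ = √[0.3123 × 0.6877 × (1/232,950 + 1/3,050)] = 0.00845
- SE₁ = √[0.312 × 0.688/232,950 + 0.332 × 0.668/3,050] = 0.00858
- power = Φ[(0.0200 − 0.01655)/0.00858] = Φ(0.40) = 65.6%

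The stated 80% is therefore not reproduced at this rate. For an increase of 2 points, power is 80.5% at a control rate of 18% and 79.7% at 18.5%, so the claim needs a rate of about 18%, which the documents do not give. If 2% is relative, power at 31.2% is about 11%.

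**Step 2. Where the variance sits.** The transportation arm contributes 0.332 × 0.668/3,050 = 7.27 × 10⁻⁵. The control arm contributes 0.312 × 0.688/232,950 = 0.09 × 10⁻⁵. The transportation share is 7.27/7.36, about 99%.

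**Step 3. Effect of adjustment.** Adjustment multiplies the variance by (1 − R²), which is the same as dividing both arm sizes by (1 − R²). Power for 2 absolute points:

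| Control rate | R² = 0 | 5% | 10% | 20% | R² needed for 80% power |
|---|---|---|---|---|---|
| 31.2% | 65.6% | 67.8% | 70.1% | 75.1% | 0.29 |
| 25% | 71.2% | 73.4% | 75.6% | 80.3% | 0.19 |
| 20% | 77.5% | 79.5% | 81.6% | 85.7% | 0.06 |

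At 31.2%, the difference detectable with 80% power falls from 2.38 points to 2.32, 2.26 and 2.13. In patient terms, R² of 5% is worth 3,050/0.95 − 3,050 ≈ 161 more transportation patients, and R² of 20% is worth 3,050/0.80 − 3,050 ≈ 762.

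**Step 4. Validity and gain by simulation.** There were 40,000 replicates per scenario, with one binary covariate and 35% assumed previously vaccinated. The adjusted estimate is the risk difference standardised over that covariate.

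| Assumed uptake, previously vaccinated vs not | R² | Unadjusted power | Adjusted power | Variance ratio |
|---|---|---|---|---|
| 45% vs 23.8% | 0.05 | 64.5–64.7% | 66.7% | 0.954 |
| 55% vs 18.4% | 0.14 | 64.5–64.7% | 71.3% | 0.863 |
| 60% vs 15.6% | 0.21 | 64.5–64.7% | 74.4% | 0.798 |

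Type I error was 4.9% to 5.1% for both tests. A separate simulation of 20,000 replicates used a stronger predictor (40% previously vaccinated, uptake 60% vs 12%, R² about 0.26). Type I error was 5.0% unadjusted and 5.2% adjusted, and power was 65% and 77%.

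**Step 5. Sensitivity to the analysed number.** If choosing one person per household left 70% of each arm (an assumption), unadjusted power at 31.2% would be 50.8%. It would be 55.0% at R² = 0.10 and 59.9% at R² = 0.20.

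**The case against.** The strongest reply is that nothing here is an error. A pre-specified difference in proportions followed by an adjusted model is an accepted plan, and readers would see an adjusted estimate anyway. That stands: this is a point about efficiency.

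Second, the size of the gain rests on an R² that the documents do not supply. They give neither the prevalence of prior vaccination nor its association with current uptake. The section 4.2 exclusion may also remove habitual vaccinees and weaken the predictor. This stands too. At R² of 5% to 10% and a 31.2% control rate, the gain is only about 2 to 5 percentage points of power.

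Third, the gap between 66% and 80% belongs to section 9.2, not to the choice of test. It shrinks if the control rate is lower. At 31.2%, adjustment closes it only if R² is about 0.3, and no R² in the range considered would rescue a 2% effect meant as relative. This is correct, and the power statement needs its own repair.

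Fourth, this is a pilot arm within a larger trial, the analysed number is uncertain, and the clinic clause concerns the secondary model. Ignoring randomisation within practice would, if anything, make the primary test conservative. These points limit the weight of the concern. None of them shows that adjustment would cost anything material, and no other section makes the adjusted analysis primary.

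**Conclusion.** The concern holds. The primary test is valid but less precise than an adjusted risk difference built from covariates that section 9.5 already lists. The standardised risk difference targets the same marginal difference in proportions, so the question the trial answers does not change.

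The benefit is modest and cannot be fixed from the documents. With a 31.2% control rate, a 2-point absolute effect and 3,050 against 232,950 analysed patients, power rises from about 66% to between 68% and 75% for R² between 5% and 20%. The lower part of that range is quite possible. At lower control rates the starting power is higher, and a smaller R² reaches 80%. The change is recommended because it costs almost nothing and helps the comparison this pilot exists to test. It is not a remedy for the section 9.2 power claim.

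**What to change.** Amend section 9.5 before outcome data are examined:

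1. **Primary analysis.** Use a covariate-adjusted risk difference on one index patient per household, for example logistic regression standardised to a risk difference with a delta-method standard error. Adjust for vaccination in the prior two seasons, age, gender, race/ethnicity and insurance.
2. **Incomplete history.** Section 4.1 admits "All patients over six months old that are members of an LACDHS managed care plan", so the youngest cannot have two prior seasons on record. Specify a missing or not-applicable category so that nobody is dropped.
3. **Practice.** State now that practice is included if families are in fact randomised within practice, instead of waiting for the retrospective results.
4. **Supporting analyses.** Keep the unadjusted difference in proportions as a sensitivity analysis. The log-binomial risk ratio can remain as a supplementary estimate.
5. **Power, separately.** Restate section 9.2 with its control rate, the scale of the 2% and the number of index patients, without relying on adjustment to reach 80%.

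The cost is SAP wording and a few lines of code. No further patients are needed, and the covariates are already in the planned model.

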The retrospective analysis will result in a randomization and personalization template that will include placeholders and calculations for the following items: a) patient contact information, b) experimental group assignment, c) message contact dates (one per month in batches of 100 patients per day), d) randomly assigned message contact channel for each contact date (e.g. phone, portal, email, SMS), e) message templates with substitutable text, f) personalized message content for each month of messages, and g) stratification and personalization data elements identified in the retrospective analysis. These templates will be populated on premises at LACDHS with data to be retrieved by the Informatics Core staff. These randomized lists will be converted to personalized, tailored messages based on Mail Merge templates or similar DHS campaign management software. After lists and personalization have been completed, they will be approved by the research team in a final cross-check. All patients that have been vaccinated will be removed from contact lists before each wave of messages is delivered. These templated assignments may be moved from Excel to DHS Reporting Software (ELM) or other campaign management software by the Informatics Core.

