9.2 Sample Size

Our power calculation suggests that we have 80% power to detect a 2% impact of each intervention.

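### Section 6.2.2 intends randomization of families within practices, but the primary test in 9.5 ignores practice and leaves any clinic term to retrospective data; at a constant allocation ratio this is only slightly conservative, and the plan does not state that ratio

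*Combined protocol and SAP*

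**What the plan says.** On randomization, section 6.2.2 allocates families to arms and adds: "We will attempt to affiliate index patients with practices, and randomize patients (families) within these practices". The randomization template in the same section carries "stratification and personalization data elements identified in the retrospective analysis", without saying which of these elements, if any, will be randomization strata. For analysis, "we will randomly select one index patient per household for analysis".

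On the primary analysis, section 9.5 says: "Primary outcomes will be evaluated as a test of differences between proportions vaccinated in control and treatment groups". It names no stratum. A log-binomial regression follows for further analyses. Its listed adjusters are age, gender, race/ethnicity, insurance and prior vaccination. Clinic is not among them and appears only as "potentially clinic random effects, depending on retrospective analysis results".

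The documents give no allocation ratio by practice, no figure for variation in vaccination between practices, and no rule for families who cannot be linked to a practice.

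**The concern.** If families are randomized within practices, practice is part of the design, and the analysis should reflect it. Section 9.5 does not do so in the primary test. In the secondary model it lets data from the 2019 to 2021 campaigns (section 1.1) decide. Past data can show how much practices differ, but not whether practice was used in the allocation.

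What is at stake depends on the ratio within practices:

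- **Same ratio everywhere.** The crude and stratified estimates coincide. The crude standard error still counts between-practice variation that the design has removed, so it is somewhat too large.
- **Ratio differs between practices.** The arms have different practice mixes, and the crude difference picks up practice differences along with the effect of the text. With a transportation arm of 3,050 against 232,950 controls, small absolute departures in a practice are large relative ones.

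**Working it through.** **Inputs from the documents.** Transportation arm 3,050 and control 232,950 (5.1), so the transportation fraction is f = 3,050/236,000 = 1.29%. Vaccination rate 31.2% (2.1). Two-sided level 0.05 (9.5). Target 2%, read as 2 percentage points (9.2). 28 practices, taken as the sites listed at the front of the protocol. The arm sizes are treated as index patients, which the documents do not confirm.

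**Assumed, because the documents give no figure.** Between-practice SD of vaccination rates: 5 to 10 points. For unequal ratios, a coefficient of variation (CV) of the transportation fraction across practices of 0.25 to 0.50.

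**The plan's own figure.** Section 9.2 states that "we have 80% power to detect a 2% impact of each intervention". A two-proportion test of 31.2% against 33.2% with these arm sizes gives 65.6%, so the figure is not reproduced. That is a separate matter. It matters here only because power in this comparison starts near 66%.

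**Case 1: same ratio in every practice.**

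- Total variance: 0.312 × 0.688 = 0.2147.
- Crude SE: √[0.2147 × (1/232,950 + 1/3,050)] = 0.00844, or 0.84 points.
- Between-practice share: 0.05²/0.2147 = 1.16%; 0.10²/0.2147 = 4.66%.
- SE ratio, crude to stratified: r = 1/√(1 − share) = 1.006 and 1.024.
- Type I error of the crude test: 2 × [1 − Φ(1.96 r)] = 4.87% and 4.47%.
- Power at 2 points, using the 31.2% variance in both arms: crude Φ(0.02 r/0.00844 − 1.96 r) = 65.95% and 66.22%; stratified Φ(0.02 r/0.00844 − 1.96) = 66.37% and 67.93%.
- Power lost: 0.42 and 1.71 points.

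**Case 2: ratios differ but are unrelated to practice rates.** The bias averages zero over possible patterns, but any one pattern shifts the crude difference by a random amount with SD of about CV × SD/√28. For SD 5 points and CV 0.25 this is 0.25 × 5/√28 = 0.24 points; for SD 10 and CV 0.50 it is 0.94 points. Simulation under no effect (28 equal practices, 4,000 runs per setting) gave:

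| Between-practice SD | CV of fraction | Crude type I error |
|---|---|---|
| 5 points | 0.25 | 5.3% |
| 5 points | 0.50 | 8.6% |
| 10 points | 0.25 | 7.7% |
| 10 points | 0.50 | 18.5% |

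**Case 3: ratios track practice rates.** Bias ≈ ρ × CV × SD/(1 − f), where ρ is the correlation between a practice's fraction and its vaccination rate.

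- At ρ = 0.3 the bias runs from 0.3 × 0.25 × 5/0.987 = 0.38 points to 0.3 × 0.50 × 10/0.987 = 1.52 points.
- At the extreme of ρ = 1, simulation gave 1.2 to 2.4 points (SD 5) and 2.5 to 4.8 points (SD 10).

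In all three cases the practice-stratified Cochran-Mantel-Haenszel test held its type I error between 4.4% and 5.4%. Simulation error at 4,000 runs is about √(0.05 × 0.95/4,000) = 0.3 points.

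These figures are for the transportation comparison only. The sizes of the text-enhancement arms are not given, but the same primary test applies to them.

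**The case against.** Section 6.2.2 states an attempt, not a commitment. If affiliation fails and families are randomized without regard to practice, a simple two-proportion test on one index patient per household is the matching analysis. That stands, and the fix is conditional for this reason.

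A reader might infer that the crude analysis would bias the result, for example by supposing a fixed quota of 3,050/28 ≈ 109 transportation patients per practice. The documents do not support this. Section 5.1 gives arm totals only, and no section describes a quota or unequal ratios. Systematic bias also needs ratios that go with practice vaccination rates, about which nothing is said. Cases 2 and 3 show what could happen, not what the plan prescribes.

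A reader might also infer that error bars that ignore practice are too narrow. At a constant ratio they are slightly too wide.

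Nor does reliance on the retrospective analysis mean that trial outcomes could steer the model. Section 1.1 places that analysis before the trial, so the choice can be fixed before any outcome is seen. What remains is incomplete prespecification on the wrong criterion.

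Finally, the further elements in the template are not shown to be randomization strata, so it would be wrong to stratify on all of them by default.

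**Conclusion.** The mismatch is real but modest. The plan intends to randomize within practices, does not carry practice into the primary test, and makes the only clinic term optional for a reason unrelated to the allocation. With a constant ratio the crude test stays valid and gives up a little precision: at most a 2.4% larger standard error and 1.7 points of power over the assumed SD range of 5 to 10 points. Inflated type I error or bias arises only if ratios differ between practices, which the documents leave open. Those larger figures rest wholly on assumed SDs, CVs and correlations. The case for changing the plan is that stratification costs almost nothing in the first situation and protects the comparison in the second.

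**What to change.** In 6.2.2, state whether practice is a randomization stratum, state the allocation ratio within practices (or commit to reporting it), and give a rule for families who cannot be linked to a practice.

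In 9.5, if randomization is within practices:

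- Make the primary analysis a Mantel-Haenszel risk difference and test stratified by practice. Add only those other elements actually used as strata on the randomization list, and treat unaffiliated families as their own stratum.
- Include practice in the regression on the same basis, and delete the clause that ties it to the retrospective results.

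If practice is not used in the randomization, say so and keep the simple test.

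The cost is wording plus one stratum variable. There is a small downside. At f = 1.29%, a stratum with fewer than about 1/0.0129 ≈ 77 index patients expects less than one transportation patient, and a stratum with none contributes nothing to that comparison. Finely crossed strata should therefore be avoided.

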1. STUDY OBJECTIVES

1.1 Primary Objectives

The primary objectives are to 1) Conduct a Retrospective analysis of influenza and COVID-19 Messaging Strategies and Social Determinants of Non-Compliance. Between 2019 and 2021, DHS conducted a series of campaigns related to COVID and influenza vaccines with the objective of increasing community trust with geographically and demographically targeted advertisements. The 2021 campaign messages also adopted “Flu shot reserved for you” language that was found to be comparatively effective in Milkman et al., 2021.¹ We will also investigate disparities between the UCLA and DHS populations, 2) Develop Targeted Vaccination Promotion Approaches that Apply Principles of Behavioral Economics. We will use the results of Aim 1 to craft messages that (a) are consistent with evidence-based behavioral principles, and (b) promote “sludge reduction” mechanisms. These may include personalized messages about the easiest ways for patients to obtain free vaccinations - pharmacies closer to patients' homes and free transportation to healthcare facilities that have not been promoted at DHS in the past. Based on the retrospective analysis, we will vary the messenger identity and message content and tailor to specific subgroups. Additionally, we will use this time period to engage other large public service delivery systems that might participate in a proposal for a future multisystem RCT, 3) Conduct a Randomized Controlled Trial of Message Candidates in 2022-2023 Flu Season. The new messaging will be added to an ongoing RCT being conducted at DHS in a factorial design. The original study, limited to use of the patient portal to deliver messages, will be augmented with our approach and interventions, which will also incorporate paper mail, text messages, and call centers.

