10. DATA COLLECTION AND QUALITY ASSURANCE

10.1 Data Collection Forms

Data will be collected from LACDHS electronic medical records and CAIR2 data.

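### The adjusted models in 9.5 merge two prior seasons into one yes/no indicator, which can give up some precision in supportive estimates; the primary test is unaffected

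*Combined protocol and SAP*

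**What the plan says.** Section 9.5 (Data Analyses) has two layers. The first is the primary comparison: "Primary outcomes will be evaluated as a test of differences between proportions vaccinated in control and treatment groups". It carries no covariates.

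The second is supportive: "For further analyses, we will use multivariable log-binomial regression models". These models adjust for age, gender, race/ethnicity, insurance and "whether the patient was vaccinated in at least one of the prior two flu seasons". No reason is given for combining the seasons, and no finer coding appears elsewhere.

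On data sources, section 10.1 says: "Data will be collected from LACDHS electronic medical records and CAIR2 data". Earlier seasons are also relevant to Aim 1, a retrospective analysis described in 1.1: "Between 2019 and 2021, DHS conducted a series of campaigns related to COVID and influenza vaccines". Section 9.2 claims that "we have 80% power to detect a 2% impact of each intervention" and mentions no covariate adjustment.

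**The concern.** The indicator is the logical OR of two season-specific statuses. A 'no' can be assigned only after both seasons have been searched, so the season-level information should be available when the covariate is derived. That is an inference from the definition, supported by 10.1 and 1.1.

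The indicator then pools three histories: both seasons, last season only, two seasons ago only. If current-season uptake differs among them, part of the predictable outcome variation is left unexplained. The four-level history contains the planned indicator as a special case, so in large samples it cannot be less precise, and it is more precise whenever the three groups differ.

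At stake is the width of the adjusted intervals, chiefly for the transportation arm. With 3,050 patients against 232,950, almost all the variance comes from the smaller arm.

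**Working it through.** **Inputs from the documents.** Uptake p = 31.2% (2.1, a background figure). Arms: "Control arm: Standard Texts (n=232,950") and 3,050 in the transportation arm (5.1). Two-sided level 0.05 for transportation (9.5). A 2-point absolute effect (9.2 says 2% without stating absolute or relative).

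**Assumed.** The association between seasons, which no document gives, and 31.2% uptake in every season.

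**Step 1: the plan's own figure.** Unadjusted power, normal approximation with pooled variance under the null:

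- Null SE = √[0.3123 × 0.6877 × (1/3,050 + 1/232,950)] = 0.00845
- Alternative SE = √[0.332 × 0.668/3,050 + 0.312 × 0.688/232,950] = 0.00858
- z = (0.02 − 1.96 × 0.00845)/0.00858 = 0.40, so power is 65.6%

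The stated 80% does not reproduce for this arm on these inputs. That is a separate matter. Here 65.6% serves only as the unadjusted baseline.

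**Step 2: formulas.** For history cells with share π and current uptake q:

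- Residual variance, four-level: W4 = Σ π q(1−q)
- Residual variance, single indicator: W1, the same sum with the three vaccinated cells replaced by one cell at their average uptake
- R² = 1 − W/[p(1−p)]; variance ratio = W1/W4; reduction = 1 − W4/W1
- Adjusted power: both SEs in step 1 multiplied by √(1−R²)

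**Step 3: a weak gradient, by hand.** Order of cells: neither, two seasons ago only, last season only, both. Assumed shares 0.60, 0.10, 0.12, 0.18; assumed uptake 24%, 35%, 38%, 50%.

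- W4 = 0.1094 + 0.0228 + 0.0283 + 0.0450 = 0.2055
- Average uptake of the ever-vaccinated = 0.1706/0.40 = 42.65%; W1 = 0.1094 + 0.40 × 0.4265 × 0.5735 = 0.2073
- Ratio = 1.009, a reduction of 0.9%; power 67.3% to 67.7%

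With equal uptake in the three vaccinated cells (15%, then 53% in each), W1 = W4 and the gain is zero.

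**Step 4: a range of correlations.** Three yes/no seasons at 31.2% each, generated from a thresholded Gaussian model tuned so that the yes/no statuses have the stated correlations. The share vaccinated in both prior seasons is p² + r p(1−p), where r is the adjacent-season correlation: 0.162, 0.205 and 0.226 for r = 0.3, 0.5 and 0.6. Each one-season-only share is p minus that.

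| Correlation, adjacent / lag-two | Uptake %: neither / two ago only / last only / both | R², single → four-level | Ratio | Reduction | Adjusted power, % |
|---|---|---|---|---|---|
| 0.3 / 0.3 | 16.9 / 39.4 / 39.4 / 63.4 | 0.110 → 0.139 | 1.033 | 3.2% | 70.6 → 72.0 |
| 0.3 / 0.2 | 19.2 / 31.2 / 45.5 / 57.8 | 0.078 → 0.103 | 1.029 | 2.8% | 69.1 → 70.3 |
| 0.3 / 0.09 | 21.7 / 22.4 / 52.4 / 51.3 | 0.049 → 0.090 | 1.045 | 4.3% | 67.8 → 69.6 |
| 0.5 / 0.5 | 10.5 / 43.0 / 43.0 / 77.4 | 0.276 → 0.333 | 1.087 | 8.0% | 79.1 → 82.3 |
| 0.5 / 0.4 | 12.5 / 32.2 / 52.2 / 72.6 | 0.225 → 0.280 | 1.077 | 7.1% | 76.4 → 79.3 |
| 0.6 / 0.6 | 7.9 / 44.6 / 44.6 / 83.1 | 0.383 → 0.450 | 1.122 | 10.9% | 85.0 → 88.8 |
| 0.6 / 0.36 | 12.3 / 13.9 / 73.9 / 71.9 | 0.252 → 0.360 | 1.169 | 14.4% | 77.8 → 83.8 |

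The largest reduction comes when the lag-two correlation is well below the adjacent one, not where R² is highest.

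**Step 5: the planned scale.** In a correctly specified log-binomial model, information on the log risk ratio is proportional to Σ π q/(1−q). In the weak case this is 0.487 for the single indicator and 0.497 for four levels, a ratio of 1.02. It rises by about 7% to 10% at adjacent correlation 0.3 and 24% to 35% at 0.5. The risk-scale figures are therefore not an overstatement for the planned model in these cases, but they are not its exact interval widths either.

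**The case against.** The strongest reply is that no decision rests on this covariate. The primary test is unadjusted, the log-binomial models are further analyses, and 9.2 does not rely on adjustment. That stands. A reader might infer that the trial loses primary power, or that the collapsed indicator biases the comparison. The documents support neither: the indicator is prespecified and fixed before treatment, so using it is legitimate.

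A reader might also infer that the subgroup analysis cannot separate habitual from occasional vaccinees. Section 9.5 plans subgroup interactions but names no subgroups, and nothing makes prior vaccination one of them. That inference should not be drawn.

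The size is wholly assumed, and this too stands. Section 4.2 excludes patients already vaccinated this season. If these are mostly habitual vaccinees, the gradient among those analysed is weaker. Section 6.2.2 analyses one index patient per household, with no household count, so the powers above are optimistic. The variance ratio itself does not depend on the sample size.

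Nor is the finer coding entirely free. Eligibility starts at six months of age and requires only that patients "have had contact with the health system in the past 2 years" (4.1), so some histories are short or incomplete. A single record satisfies the planned indicator, whereas a missed record turns 'both' into 'one only'. Fitted risks closer to 1 can also strain log-binomial convergence. These are small costs and do not reverse the conclusion.

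**Conclusion.** The point holds as an optional efficiency improvement to the supportive adjusted models. Its direction is secure: in large samples the four-level history cannot lose precision and gains whenever uptake differs among the three vaccinated histories.

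Its size is not known. Risk-scale residual variance falls by about 3% to 14%, or about 1 to 6 points of adjusted power for a 2-point effect. This assumes correlations of 0.3 to 0.6 between adjacent seasons, lag-two correlation equal or lower, 31.2% uptake each season, the full arm sizes as analysed counts, and no other covariates. Other covariates would reduce the gain somewhat. Neither end is a bound: a weak gradient gives about 1%, and equal uptake across the vaccinated histories gives none.

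The primary comparison, its validity and the 9.2 power statement are untouched.

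**What to change.** In 9.5, replace the single indicator with a four-level prior-vaccination history: neither season, last season only, two seasons ago only, both. State that a season with no record, or before the patient was eligible for vaccination, is coded as not vaccinated, which is what the present indicator does implicitly. Prespecify a fallback, for example modified Poisson regression with robust standard errors, if the log-binomial model does not converge.

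The change needs no new data source and should be fixed before outcomes are analysed. It costs two extra parameters, some misclassification of 'both' as 'one only' where records are incomplete, and a convergence check.
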